4.2.2. Time to Vision Loss Analysis

In the evaluation of vision, BCVA is an important measurement tool to assess the changes over time. However, substantial differences in mean change of visual acuity between treatment and sham are difficult to demonstrate within the timeframe of a clinical trial in patients with GA. Nonetheless, at various time points in the study, patients can experience a significant and permanent drop in visual acuity. Hence, it is more appropriate to analyze vision data by using the time-to-event analysis to better characterize patient's vision loss by accounting for instances of clinically significant vision loss in terms of change in BCVA Scores (ETDRS Letters) from Baseline to Month 24. In this time-to-event analysis, a vision loss event was defined as a loss of ≥ 15 letters (equivalent to a loss of 3 lines on the ETDRS chart) in BCVA from Baseline measured at any two or more consecutive visits up to Month 24. These parameters were chosen as a 3-line BCVA loss (equivalent to doubling of visual angle) is widely recognized as a significant deterioration in vision and a minimum of two consecutive visits is representative of persistent disease progression. The framework of this analysis is formulated as the secondary Estimand below.

4.2.2.1. Definition of the Estimand

This secondary efficacy objective is to demonstrate that ACP 2 mg can significantly reduce the rate of persistent vision loss compared to Sham up to Month 24.

The following 5 attributes define the secondary Estimand for the secondary endpoint evaluation:

A. Population:

Subjects with geographic atrophy secondary to dry age-related macular degeneration. Analysis will be performed on all randomized patients who received at least one dose of study drug (ITT population).

B. Interventions:

ACP 2mg versus Sham.

C. Endpoint:

Time to persistent vision loss (BCVA ≥ 15 letters loss from Baseline at 2 or more consecutive visits) during the study from Baseline to Month 24.

D. Intercurrent events (ICE's) and strategies:

1. Treatment changes (i.e., interruptions, non-adherence, dose changes, discontinuation): "treatment policy" – i.e., treatment changes will be ignored, and all data collected will contribute to the analysis regardless of whether these follow such ICE's.
2. COVID-19: "treatment policy" – i.e., impact of COVID-19 pandemic will be ignored, and all data collected will contribute to the analysis regardless of whether these follow such ICE's.

E. Population-level summary:

Cumulative rate of persistent vision loss

4.2.2.2. Vision Analysis Method

Time-to-vision loss is defined as the time to the first occurrence of BCVA \geq 15 letters loss from Baseline in 2 or more consecutive visits for the ITT population. Subjects without vision loss event are censored at the last assessment of BCVA prior to the end of the study, or at the randomization if no post baseline BCVA assessment is available.

Time-to-event analysis will be conducted using Kaplan-Meier method with a log-rank test and a Cox proportional hazards regression model with the hazard ratio and associated two-sided 95% confidence interval. Statistical significance of testing with the p-value from the log-rank test will be used in the hierarchical testing procedure.

4.2.2.3. Sensitivity Vision Analyses

Recognizing that time-to-vision loss analysis depends on the thresholds of the loss of ETDRS letters, the following sensitivity analyses on different thresholds will be performed:

- Sensitivity vision loss thresholds: BCVA \geq 10 or 20 letters loss from Baseline at 2 or more consecutive visits

Similar analyses using time-to-first event will be used.

4.2.2.4. Supportive Vision Analyses

In addition, the following analyses will be conducted.

- Vision loss thresholds: BCVA \geq 10, 15 or 20 letters loss from Baseline in at least one visit. Similar analyses using time-to-first event will be used.
- Vision loss as a categorical response (BCVA \geq 15 letters of loss from Baseline) at Month 24. Statistical test (Chi-squared) will be conducted.

4.2.3. Other Secondary Endpoints

4.2.3.1. Mean change in best corrected visual acuity (BCVA in ETDRS letters) from Baseline to Month 24.

ACP 2mg vs. Sham will be compared using MMRM model with change from Baseline as the response, with visit, treatment, and treatment by visit interaction as fixed effects, subject as random effect using the ITT population. Treatment groups include ACP 2mg and Sham in the ITT population.

4.2.3.2. Mean change in low luminance best corrected visual acuity (LL BCVA in ETDRS letters) from Baseline to Month 24.

The endpoint will be analyzed similarly as in the BCVA described above with change from Baseline of LL BCVA as the response variable.

4.2.3.3.

CCI

4.2.3.4.

CCI

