11.5 Randomization Procedure

Patients will be centrally allocated to one of the two treatment groups by a dynamic minimization procedure using clinical site in a 1:1 ratio stratified by factors known to be of prognostic importance in AMD:

- Baseline visual acuity < 50 ETDRS letters (20/100 Snellen equivalent) vs \geq 50 ETDRS letters
- Size of Baseline geographic atrophy (< 4 disc areas vs \geq 4 disc areas)
- Pattern of Fundus Auto Fluorescence (FAF) at the junctional zone of GA (None/focal vs banded/diffuse)

Patients initially randomized to Zimura 2 mg at Day 1 will be re-randomized at Month 12 in 1:1 ratio to Zimura 2 mg monthly vs every other month (please see 11.1 Study Design) using the same minimization procedure as for the initial randomization (i.e. using the same factors at Baseline).

Randomization will be performed using an IRT system based on the stratification information above to randomize each subject and assign a treatment arm.

The IRT system will be used to assign masked study kits to patients throughout the duration of the trial. All study medication must be dispensed using the IRT system. At each dispensing visit the IRT system will allocate each study drug kit(s) using the kit number on the label of the study medication kit.

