11.7.4 Efficacy Analysis

The efficacy analysis will be conducted on all randomized and treated patients according to the intention-to-treat principle.

For normal endpoints, treatment groups will be compared through an analysis of variance including stratification factors.

For binary endpoints, treatment groups will be compared through Mantel-Haenszel or Cochran-Mantel-Haenszel χ^2 tests adjusting for stratification factors.

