1.3. Study Period and Visit Window Definition

Study assessments in Year 2 are summarized below.

Year 2

2. Statistical Hypotheses

The following hypothesis testing will be conducted sequentially.

1. Hypothesis testing in EM vs. Sham for mean GA growth rate are:

$$H_0: \Delta = 0$$

$$\text{versus } H_1: \Delta \neq 0,$$

where $\Delta = \mu_1 - \mu_2$, μ_i is the mean growth rate (slope) of GA over 24 months for treatment EM, or Sham, respectively.

2. Hypothesis testing in ACP 2mg vs Sham for time to vision loss will be conducted using Kaplan-Meier method with a log-rank test
3. Hypothesis testing in EOM vs. Sham for mean GA growth: similarly, as in (1)
4. Hypothesis testing in ACP 2mg vs Sham for mean change in best corrected visual acuity (BCVA in ETDRS letters) from Baseline to Month 24
5. Hypothesis testing in ACP 2mg vs Sham for mean change in low luminance best corrected visual acuity (LL BCVA in ETDRS letters) from Baseline to Month 24

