6. CCI

The hypothesis testing will be evaluated according to a pre-specified hierarchical testing procedure to control overall type-1 error at a 5% two-sided significance level. If the primary analysis testing GA growth rate (ACP 2mg vs Sham) based on Year 1 data is statistically significant, the hypotheses tests will be performed in a sequential way as described above to control familywise type I error rate with 2-sided significance level of 0.05. A test will be performed only if all the preceding tests are statistically significant.

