4.2.1.2. Statistical Method

With a re-randomization at the end of Year 1, the initial stratification factors from the randomization are no longer applicable in the analysis of Year 2. Therefore, the stratifications factors will be removed from the MMRM model as in the primary analysis.

The revised model is described below.

A mixed model for repeated measures (MMRM) will be applied to all available data, using response variable of the GA growth area over time up to Month 24 in 5 time points: Baseline, Month 6, Month 12, Month 18, and Month 24. The MMRM will be used to assess the difference between the treatment groups in terms of the rate of growth (slope) of the GA over time of 24 months. Time is defined as a continuous variable in number of study days since the baseline assessment. Treatment groups include ACP EM, ACP EOM, and Sham. A model will be fitted

by using restricted maximum likelihood (REML) and include time, treatment, and treatment by time interaction as fixed effects, subject as random effect.

Notice that in the primary analysis at Year 1 (Month 12), the square root transformation of GA growth area was used. However, the mean GA growth (slope) has shown similar results with or without square root transformation. In addition, it is difficult to interpret the transformed data in context. Therefore, in the Year 2 analysis, the untransformed GA growth using observed GA area of measurement will be used as the primary endpoint.

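### The Year 2 BCVA and low-luminance BCVA models omit the baseline score, which leaves the tests valid but gives up precision in hypotheses 4 and 5

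*SAP*

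**What the plan says.** Year 2 SAP 4.2.3.1 takes change from baseline in BCVA as the response and fits an MMRM "with visit, treatment, and treatment by visit interaction as fixed effects, subject as random effect using the ITT population". The groups are ACP 2 mg and Sham as allocated on Day 1. Section 4.2.3.2 adds: "The endpoint will be analyzed similarly as in the BCVA described above with change from Baseline of LL BCVA as the response variable". These sentences are complete in the readable text, so redaction does not explain the missing terms. The addendum reproduced in section 5.2 likewise says the ranked Year 2 tests use an MMRM like that of Year 1 with the stratification factors removed.

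Both endpoints are numbered tests in Year 2 SAP section 2. Hypothesis 4 is "Hypothesis testing in ACP 2mg vs Sham for mean change in best corrected visual acuity (BCVA in ETDRS letters) from Baseline to Month 24"; hypothesis 5 is "Hypothesis testing in ACP 2mg vs Sham for mean change in low luminance best corrected visual acuity (LL BCVA in ETDRS letters". The sequence is fixed: "A test will be performed only if all the preceding tests are statistically significant".

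The reason for dropping the factors appears in Year 2 SAP 4.2.1.2, for the GA growth model: "the initial stratification factors from the randomization are no longer applicable in the analysis of Year 2". The version history gives the same reason for the revised MMRM. Section 4.2.3 and the addendum give none.

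Protocol 11.5 describes an allocation "stratified by factors known to be of prognostic importance in AMD", and baseline visual acuity (below 50 letters, or 50 and above) is one of those factors. The Month 12 re-randomisation uses the same baseline factors. For normal endpoints, Protocol 11.7.4 says "treatment groups will be compared through an analysis of variance including stratification factors". The Year 1 primary model keeps the baseline VA stratum and FAF pattern, each with a time interaction, and leaves out GA size. Year 2 SAP 4.5, which lists departures from the protocol's analyses, does not mention removing the factors.

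**The concern.** Baseline acuity is on hand for these analyses. BCVA is averaged over Screening and Day 1 when both are available (Year 2 SAP 4.1.9), and LL BCVA is measured on Day 1. Where change is related to baseline, leaving the score out keeps explainable variance in the residual and lets a realised baseline difference between arms show up as a difference in change.

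The stated reason does not reach these two tests. Re-randomisation at Month 12 splits the ACP arm into two regimens, but hypotheses 4 and 5 pool that arm again and test the Day 1 randomised comparison. The reason also says nothing about a continuous baseline score.

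What is at stake is power. A miss on hypothesis 4 closes hypothesis 5 and the redacted test after it. Year 2 SAP 4.2.2 itself expects mean acuity differences to be hard to show in a trial of this length.

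**Working it through.** **The plan's own figure.** The readable text gives no power, SD or effect size for BCVA or LL BCVA. The only stated power is for the primary GA slope: 97% for 0.11 mm with about 400 patients, and significance at an estimate of 0.057 mm. Taking 200 per arm, SE = 0.057/1.96 = 0.0291 and SD = 0.0291/√(2/200) = 0.291 mm, which gives 96.6% power at two-sided 0.05. The figure reproduces. Because the SD is back-solved, this is only a consistency check, and it says nothing about acuity.

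**Variance of the treatment difference at Month 24.** Let σ be the baseline SD, kσ the Month 24 SD and r their correlation. The calculation takes Month 24 as a single visit with complete data. Per patient:

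- change, no baseline term: σ²(1 + k² − 2rk)
- change, baseline score in the model: σ²k²(1 − r²)
- ratio, adjusted to unadjusted: k²(1 − r²)/(1 + k² − 2rk), which becomes (1 + r)/2 when k = 1.

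Neither r nor k is in the documents. Over an assumed range, the variance saved (1 minus the ratio) is:

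| r | k = 1 | k = 1.2 | k = 1.4 |
|---|---|---|---|
| 0.5 | 25% | 13% | 6% |
| 0.7 | 15% | 3% | 0% |
| 0.8 | 10% | 0.3% | 2% |
| 0.9 | 5% | 2% | 15% |

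Example: r = 0.7, k = 1.2 gives 1.44 × 0.51/(2.44 − 1.68) = 0.734/0.760 = 0.966.

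**In patients and power, for k = 1 only.** 400 divided by the ratio is 400/0.75 = 533, 400/0.85 = 471 and 400/0.95 = 421 patients at r = 0.5, 0.7 and 0.9. A test with 80% power unadjusted would have Φ(2.802/√ratio − 1.960) = 90%, 86% and 82%.

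**Conditional shift.** The slope of change on baseline is rk − 1. Each letter by which the arms differ at baseline therefore moves the unadjusted estimate by (1 − rk) letters, against the arm that starts higher when rk is below 1. With k = 1 this is 0.5, 0.3 and 0.1 letters at r = 0.5, 0.7 and 0.9. At r = 0.8, k = 1.2 it is 0.04. At r = 0.9, k = 1.4 it is 0.26 in the other direction. For scale, an assumed baseline SD of 10 to 15 letters and 200 per arm give a baseline-difference SE of SD × √(2/200) = 1.0 to 1.5 letters under simple randomisation, a 95% range of about ±2.0 to ±2.9. Minimisation on the VA split removes part of this.

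**Validity and what the stratum recovers.** A simulation used 400 patients, 4,000 runs per setting, one visit, k = 1, an assumed baseline mean of 65 and SD of 12 letters, and allocation balanced within the 50-letter split as a stand-in for the minimisation.

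| r | SE, no covariate | SE, VA stratum | SE, baseline score | Type I error, no covariate |
|---|---|---|---|---|
| 0.5 | 1.199 | 1.145 | 1.040 | 4.1% |
| 0.7 | 0.929 | 0.904 | 0.857 | 4.7% |
| 0.9 | 0.536 | 0.531 | 0.523 | 4.8% |

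The unadjusted test does not exceed 5%, and the continuous score recovers more than the stratum.

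**The case against.** The strongest reply is that the gain may be very small. The (1 + r)/2 rule needs equal SDs. Entry acuity is restricted (Protocol 10.2.3 sets a Snellen range and excludes changes of 5 letters or more between Screening and Day 1), with no such limit later. Year 2 SAP 4.2.2 expects some patients to have large, lasting losses. Both suggest k above 1, where the table shows savings near zero for several values of r. A two-visit mean baseline also tends to raise r. This stands: 25% is the top of the range, not an expected value.

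Second, the addendum dropped the factors while Year 1 was still masked (approved 3 August 2022), whereas Year 2 SAP version 2.0 postdates the Year 1 analysis. Monthly BCVA from Month 1 enters the model, so part of the response data had been unmasked. This also stands: the change has to be declared as made after Year 1.

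Third, the protocol lists BCVA and LL BCVA as safety variables, so it is arguable whether 11.7.4 binds here. It is, but the Year 2 SAP places both under efficacy, in its confirmatory sequence. Protocol 11.7.4 in any case asks for the factors, not the continuous score, so leaving out the score is not itself a protocol departure.

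Finally, the tests are reached only if hypotheses 1 to 3 succeed. That limits the consequence but does not support the omission.

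**Conclusion.** The point holds as one of efficiency and consistency. The models leave out a baseline measurement already collected, and the reason given for dropping the factors does not apply to a Day 1 comparison in the ITT set. The cost is about 0 to 25% of the variance of the treatment difference, resting on assumed r from 0.5 to 0.9 and k from 1 to 1.4.

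A reader might infer that the treatment estimate is biased or the false-positive rate inflated. The documents do not support that: allocation is randomised and minimised on baseline VA, the unadjusted contrast is unbiased over randomisations, and the simulated type I error is at or below 5%. The shift of (1 − rk) letters is conditional on the imbalance that happens to occur. Nor can any change to a trial conclusion be shown, since no acuity effect size or power is stated. The Year 1 acuity models are redacted, so whether they adjusted for baseline cannot be checked.

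**What to change.** Before Month 24 unmasking, add continuous baseline BCVA (or baseline LL BCVA) and its interaction with visit as fixed effects in the models of 4.2.3.1 and 4.2.3.2. This does most of the work.

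Optionally, also keep the Day 1 factors used in the Year 1 primary model: FAF pattern in both models, and the baseline VA stratum for LL BCVA (in the BCVA model the continuous score already carries that information). GA size is not needed. If it is added, use the corrected values, because the Year 1 SAP reports that 38 patients were placed in the wrong size stratum.

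In section 4.5, list two items: the removal of the stratification factors named in Protocol 11.7.4, with a reason that fits the Day 1 comparison, and this change from the addendum, stated as made after the Year 1 analysis. The cost is a few lines of SAP text and that disclosure. No new data are needed.

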4.3. Safety Analyses

All safety analyses will be performed on the Safety population and Re-randomized population. The analyses will be conducted according to the treatment that they received. However, subjects who have ever received an injection of ACP will be analyzed in the ACP group. Missing values of safety data will not be imputed, and safety summaries will be based on the observed cases.

4.3.1. Extent of Exposure

Exposure to study medication will be evaluated for each treatment group with respect to treatment duration (= Last injection date - First injection date + 30, in days), number of subjects treated at each planned visit, total injections received, using descriptive statistics (N, mean, standard deviation, median, minimum, Q1, Q3, maximum).

4.3.2. Adverse Events

Adverse events (AEs) will be recorded starting after the first dose of study drug and continuing until 30 days after the last dose or until the last follow-up visit required by the protocol, whichever comes later. Treatment-emergent AEs (TEAE) will be used and be evaluated for each treatment group.

All AEs will be coded using MedDRA (version 25.1 or latest) terms.

- An overview of TEAEs will be provided. In addition, the number and percentage of patients with TEAEs will be tabulated for each treatment group and in total by system organ class (SOC) and preferred term (PT). The number and percentage of the subjects who experienced at least one TEAE will be included. Subjects will only be counted once for each preferred term. In case that a subject experienced the same event more than once, the worst severity will be presented.
- Tabular summaries of the following AEs will be provided by SOC and PT:
 - Summary of TEAEs
 - Summary of TEAE of special interest (AESI)
 - All TEAEs regardless of the relationship to study treatment
 - All TEAEs regardless of the relationship to study treatment with frequency of $\geq 5\%$ in any treatment arm.
 - TEAEs related to study treatment
 - TEAEs related to injection procedure
 - TEAEs by the maximum severity grade
 - TEAEs related to study treatment by the maximum severity grade
 - TEAEs related to injection procedure by the maximum severity grade

- Ocular TEAEs by study eye and fellow eye
- Treatment related Ocular TEAEs by study eye and fellow eye
- Injection procedure related Ocular TEAEs by study eye and fellow eye
- Ocular TEAEs (study eye) by the maximum severity grade
- Treatment related Ocular TEAEs (study eye) by the maximum severity grade
- Injection procedure related Ocular TEAEs (study eye) by the maximum severity grade
- TEAEs with high level term of cataract conditions by study eye and fellow eye
- TEAEs leading to discontinuation of study drug
- Treatment related TEAEs leading to discontinuation of study drug
- Injection procedure related TEAEs leading to discontinuation of study drug
- Ocular TEAEs (study eye) leading to discontinuation of study drug
- TEAEs leading to death
- Treatment related TEAEs leading to death
- Injection procedure related TEAEs leading to death
- All AEs, including non-TEAEs, will be included in individual subject listings.
 - The listings will include the subject identifier, age, sex, verbatim term, preferred term, eye (N/A/OD/OS/OU), serious (yes/no), date of onset, relative study day of onset, onset before injection, after first injection or after second injection, duration of the event (or continuing), severity (mild/moderate/severe), causality (relationship to study medication/injection procedure), action taken (study drug permanently discontinued: yes/no), treatment (yes/no), and outcome (resolved/not resolved/fatal).
 - The same listings will be provided separately for severe AEs, AEs leading to permanent discontinuation of the study treatment, and for AEs leading to death.

4.3.3. Serious Adverse Events

Treatment-Emergent Serious adverse events (SAEs) will be summarized by system organ class and preferred term. The number and percentage of the subjects who experienced at least one SAE will be included.

SAE data will be evaluated for each treatment group.

Tabular summaries of the following SAEs will be provided:

- All SAEs regardless of the relationship to study treatment
 - related to study treatment
 - related to injection procedure
- Ocular SAEs (study eye) regardless of the relationship to study treatment
 - related to study treatment (SE)
 - related to injection procedure (SE)

In addition, separate listings will be created for deaths and all SAEs. List for SAEs will include the subject identifier, age, sex, verbatim term, preferred term, eye (N/A/OD/OS/OU), serious (yes/no), date of onset, relative study day of onset, onset before injection, after first injection, duration of the event (or continuing), severity (mild/moderate/severe), causality (relationship to study medication/injection procedure), action taken (study drug permanently discontinued: yes/no), treatment (yes/no), and outcome (resolved/not resolved/fatal).

Vital Signs

Descriptive statistics at each time point up through and including the Month 24 visit will be used to display the changes from Baseline for pulse and blood pressure (systolic and diastolic). Mean change of pulse and blood pressure (systolic and diastolic) from Baseline to the last measurement will be provided.

